6.2 Clinical Laboratory Parameters

Descriptive statistics for clinical laboratory values in Table 4 (in SI units) and changes from the baseline values at each assessment time point will be presented by treatment for the following laboratory parameters, measured at Screening visit (Days -28 to -2), Day -1, post-dose Days 4 and 20 of each treatment period and Day 69 (end of study).

Hematology and Coagulation	Serum Chemistry	Urinalysis	Additional Tests				
Hemoglobin	Sodium	pН	Serology: anti-HIV-1/2, HBsAg,				
Hematocrit	Potassium	Specific gravity	anti-HCV				
Erythrocytes	Chloride	Color					
Platelets	Calcium	Protein	FSH test				
Leukocytes	Inorganic phosphate	Glucose	for postmenopausal women,				
Neutrophils	Urea	Ketones	menstruation was < 1 year before				
Eosinophils	Creatinine	Hemoglobin	screening				
Lymphocytes	Uric acid	(erythrocytes)					
Monocytes	Total bilirubin	Leukocytes	Serum pregnancy test for women				
Basophils	Direct bilirubin	Microscopic	of childbearing potential,				
INR	ALT	analysis, if urine is	menstruation was < 1 year before				
aPTT	AST	leukocytes or hemoglobin	screening				
РТ	GGT						
	AP						
	LDH		Urine drugs of abuse test				
	СРК		including but not limited to				
	Amylase		methamphetamines, opiates,				
	Lipase		methadone, cocaine,				
	Triglycerides		benzodiazepines, and barbiturates				
	Total cholesterol						
	HDL cholesterol						
	LDL cholesterol						
	Total protein						
	Albumin		Alcohol breath test				
	Glucose						

Table 4:Clinical Laboratory Tests

INR: International Normalized Ratio; aPPT: Activated Partial Thromboplastin Time; PT: Prothrombin Time; ALT: Alanine Aminotransferase; AST: Aspartate Aminotransferase; GGT: Gamma-glutamyl Transferase; AP: Alkaline Phosphatase; LDH: Lactate Dehydrogenase; CPK: Creatine Phosphokinase; HDL: High Density Lipoprotein; LDL: Low Density Lipoprotein; HIV: Human Immunodeficiency Virus; HBsAg: Hepatitis B Surface Antigen; HCV: Hepatitis C virus. Smoking history and Drug of Abuse/Alcohol Screen will be measured at Screening visit and Day -1 visits.

The following clinical laboratory levels will be measured at Screening only:

- Serology: HIV-1/HIV-2 antibody, HbsAg and Anti-HCV
- FSH and Pregnancy Test for female subjects

A shift table from baseline to worst postbaseline evaluations will be presented by treatment for the following categories: low, normal, and high. The denominators for calculating the percentages will be based on the number of subjects with non-missing assessments at Baseline and at least 1 post-baseline value for each parameter.

Unscheduled assessments that are not used as Baseline will not be included in summary tables except in the shift summaries; however, all clinical laboratory values will be presented in a data listing, in chronological order, or by date for unscheduled values.

The actual values of clinical laboratory evaluations, date of collection/time, and reference range and clinical significance will be listed for each visit.

6.3 Vital Signs

Descriptive statistics for actual values and changes from Baseline for vital signs (systolic and diastolic blood pressures, heart rate, respiratory rate, and temperature in supine position) will be summarized at Screening visit (Days -28 to -2), pre-dose on Day 1, post-dose on Days 4, 6, 9, 12, 16, 20 of each treatment period and Day 69 (end of study).

The actual values of vital signs, date of collection/time, reference ranges, and clinical significance will be listed for each scheduled visit.

6.4 Safety 12-Lead Electrocardiogram

ECG parameters (heart rate (HR), RR, PR, QT, QTc intervals, and QRS duration) collected at Screening visit (Days -28 to -2), and Day -1 (prior to study drug administration) will be provided in a listing.

The actual values of ECG parameters, date of collection/time, reference ranges, and clinical significance will be listed for each scheduled time point and visit.

6.7 Columbia Suicide Severity Rating Scale

For the Columbia-Suicide Severity Rating Scale (C-SSRS), the number and percentage of subjects with suicidal ideation and suicidal behavior before the study treatment (life time history and past 6 months) and after study treatment (treatment period) will be summarized by treatment for the Safety population.

SKLYKP3089		SK Life Science, Inc.
SKLYKP3089C037	Statistical Analysis Plan	Page 23

The distribution of the most severe suicidal ideation and suicidal behavior will also be presented for life history, in the past 6 months and after study treatment. Any subjects with postbaseline suicidal ideation or suicidal behavior will be included in a data listing and a separate listing will include any reported AEs. A listing of C-SSRS data for all subjects will also be provided, which will include subject number, treatment, visit, intensity of suicidal ideation, suicidal behavior type and lethality of suicidal behavior, in chronological order.

6.8 Other Safety Assessments

The physical examination findings and other safety assessments will be presented in data listings. Abnormal findings will be flagged for clinical significance based on the principal investigator's (PI) judgment.

7 INTERIM ANALYSIS

No interim analysis is planned for this study.

8 GENERAL STATISTICAL CONSIDERATION FOR DATA ANALYSIS AND HANDLING

8.1 General Statistical Procedures

The descriptive statistics for continuous variables will be the number of subjects, mean, median, standard deviations (SD), minimum, and maximum. Mean and median will be reported to 1 more decimal places than the raw data, while the SD will be reported to 2 more decimal places than the raw data. Minimum and maximum will be reported with the same decimal places as that of the original data.

Frequency distributions for all categorical variables will be presented using counts and percentages. Percentages will be reported to 1 decimal place.

Unless otherwise stated, denominators for calculating the percentages in shift analysis (to worst assessment) will be based on the number of subjects with non-missing values at both baseline and at least one post-baseline analysis visit in the Safety Population.

Unless otherwise stated, statistical analysis will be summarized for each treatment (and overall where indicated) using the Safety Population. Listings will be sorted by subject ID, sequence, and visit.

Missing data will not be imputed.

Reporting and analyses are performed using the SAS System, Version 9.4. The following CDISC version specified in Table 5 will be used.

Table 5. CDISC version

		SDTM/ADaM		Pinnacle
SDTM/SDTMIG	ADaM/ADaMIG	Controlled	SDTM/ADaM	21
Versions	Version	Terminology	define.xml	Validator
		2019-06-28/2018-12-		
1.4/3.2	2.1/1.1	21	2.0/2.0	2.2.0

8.2 Study Day and Baseline

Study Day is relative to treatment start date;

If analysis date \geq treatment start date,

Day = analysis date - treatment start date +1

Day 1= treatment start date

If analysis date \leq treatment start date,

Confidential and Proprietary, SK Life Science, Inc.

Day = analysis date - treatment start date +1

Day -1= day before treatment start date

There is no Day 0.

Baseline value is defined as the last available value collected before the first dose date of investigational product for all safety laboratory, safety ECG, and vital sign values, unless otherwise specified.

8.3 Data Handling Conventions

8.3.1 Repeated or Unscheduled Assessments of Safety Parameters

If a subject has repeated assessments before the start of the first treatment, the results from the final nonmissing assessment made prior to the start of the IP will be used as baseline. If a subject has repeated postbaseline assessments for that time point, the last nonmissing postbaseline assessment window will be used.

However, all assessments will be presented in the data listings.

8.3.2 Missing/Incomplete Date Conventions

8.3.2.1 Missing Date of the Last Dose of Study Treatment

When the date of the last dose of study treatment is missing for a subject in the Safety Population, all efforts should be made to obtain the date from the Investigator. If after all efforts are made it is still missing, the last available dosing record date will be used as the last dose date.

8.3.2.2 Missing Date Information for Adverse Events

The following imputation rules only apply to cases in which the start date for AEs is incomplete (i.e., partly missing).

Missing month and day

- If the year of the incomplete start date is the same as the year of the first dose of study treatment, the month and day of the first dose of study treatment will be assigned to the missing fields
- If the year of the incomplete start date is before the year of the first dose of study treatment, *December 31* will be assigned to the missing fields
- If the year of the incomplete start date is after the year of the first dose of study treatment, *January 1* will be assigned to the missing fields

Missing month only

• If only the month is missing, the day will be treated as missing and both the month and the day will be replaced according to the above procedure

Missing day only

- If the month and year of the incomplete start date are the same as the month and year of the first dose of study treatment, the day of the first dose of study treatment will be assigned to the missing day
- If either the year of the incomplete start date is before the year of the date of the first dose of study treatment or if both years are the same but the month of the incomplete start date is before the month of the date of the first dose of study treatment, the last day of the month will be assigned to the missing day
- If either the year of the incomplete start date is after the year of the date of the first dose of study treatment or if both years are the same but the month of the incomplete start date is after the month of the date of the first dose of study treatment, the first day of the month will be assigned to the missing day

If the stop date is complete and the imputed start date as above is after the stop date, the start date will be imputed by the stop date.

If the start date is completely missing and the stop date is complete, the following algorithm will be used to impute the start date:

- If the stop date is after the date of the first dose of study treatment, the date of the first dose of study treatment will be assigned to the missing start date
- If the stop date is before the date of the first dose of study treatment, the stop date will be assigned to the missing start date

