1 INTRODUCTION

This statistical analysis plan (SAP) describes the statistical analysis methods and data presentation to be used for the analysis and summarization of the safety data from Protocol SKL-YKP3089C037. The clinical pharmacology analysis plan (CPAP) which details the planned analyses for the pharmacokinetic (PK) data for this study will be a separate document.

The SAP will be finalized before database lock. Any changes made after finalization of the SAP will be documented in the clinical study report (CSR). Related documents are the study protocol and electronic case report forms.

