6.1 Adverse Events

Adverse events will be coded by system organ class and preferred term using the MedDRA, Version 23.0.

Treatment-emergent AEs (TEAEs) are defined as AEs that start or worsen (increase in severity) on or after the first dose date of study medication (Day 1) to the follow-up visit (Day 69).

If more than 1 AE is coded to the same preferred term for the same subject, the subject will be counted only once for that preferred term using the greatest severity and strictest causality for the summarization by severity and causal relationship.

Related TEAEs include all those classified by the investigator as having a possible, probable, or definite relationship to the Investigational product. Unrelated TEAEs are those events classified as unrelated or having a remote likelihood of being related to the Investigational product. If the same event occurs more than once per subject and treatment, and there is more than 1 relationship classification, the most related value will be summarized. For summaries by severity, the most severe grade will be selected.

The number and percentage of subject with TEAEs by system organ class and preferred term, and by severity, and by causal relationship to the IP, will be summarized by treatment and overall.

A listing of all AEs, along with SAEs, AEs leading to death, and AEs leading to discontinuation of IP will be provided.

The MedDRA version will be specified in a footnote in both tables and data listings.

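### Incomplete AE onset dates are imputed from the first dose only, so a Period 2 or 3 event can be tabulated under an earlier treatment if AEs are assigned by onset date

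*SAP*

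**What the plan says.** SAP 6.1 says that TEAEs, by system organ class, preferred term, severity and relationship, "will be summarized by treatment and overall". It handles repeats with the words "If the same event occurs more than once per subject and treatment". Both statements presuppose that every AE already carries treatment A, B or C. Neither SAP 6.1 nor Protocol 13.2.3 says how it gets one; both give a single window from the first dose to Day 69.

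SAP 8.3.2.2 imputes incomplete onsets as follows when the onset is not in a month or year before the first dose:

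- Month and day missing, same year as first dose: "the month and day of the first dose of study treatment will be assigned to the missing fields".
- Month only missing: "the day will be treated as missing and both the month and the day will be replaced according to the above procedure".
- Day only missing, same month as first dose: the day of the first dose.
- Day only missing, later month: "the first day of the month will be assigned to the missing day".
- Start wholly missing, stop date after first dose: "the date of the first dose of study treatment will be assigned to the missing start date".
- Cap, used only when a full stop date exists: where "the imputed start date as above is after the stop date, the start date will be imputed by the stop date".

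The doses on Days 22 and 43 appear nowhere in these rules.

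**The concern.** The imputation rules suit a study with one treatment start. Here each subject takes each treatment once, so the period of onset identifies the dose last taken. Setting a Period 2 or 3 onset to Day 1, or to the 1st of a month that falls before the relevant dose, links the event to a dose that was not the most recent one.

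The by-treatment TEAE table is an output for the secondary objective, the safety and tolerability of the tablet fasted and the suspension fasted and fed. Misplaced events would blur that comparison. Without an attribution sentence, two programmers could also follow this SAP and produce different by-treatment tables.

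**Working it through.** The plan gives no figure to reproduce, so the check applies the SAP 8.3.2.2 rules to every possible true onset day and counts those that land in the wrong period.

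**Inputs**

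- Doses on Days 1, 22 and 43 and follow-up on Day 69 (Protocol synopsis). In whole days: Period 1 = Days 1–21 (21 days), Period 2 = Days 22–42 (21 days), Period 3 = Days 43–69 (27 days). 21 + 21 + 27 = 69. A date equal to a dosing day counts in the period which that dose opens.
- Planned first enrolment 11 January 2021 and last completion 21 March 2021 (Protocol synopsis). Assumption: Day 1 is 11, 12 or 13 January. Day 69 = Day 1 + 68 days = 20, 21 or 22 March; the last fits through the ±1 day follow-up window.

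**Month missing, or start wholly missing with a stop date after first dose.** The imputed onset is Day 1. All Period 2 and 3 days are wrong: 21 + 27 = 48 of 69, for every start.

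**Only the day missing.** January onsets go to Day 1, February onsets to 1 February, March onsets to 1 March.

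| Day 1 | Day 22 | Day 43 | 1 February is | Misplaced onset days | Total of 69 |
|---|---|---|---|---|---|
| 11 Jan | 1 Feb | 22 Feb | Day 22 (Period 2) | 22–28 Feb, Period 3 to 2: 7 | 7 |
| 12 Jan | 2 Feb | 23 Feb | Day 21 (Period 1) | 2–22 Feb, Period 2 to 1: 21; 23–28 Feb, Period 3 to 1: 6 | 27 |
| 13 Jan | 3 Feb | 24 Feb | Day 20 (Period 1) | 3–23 Feb, Period 2 to 1: 21; 24–28 Feb, Period 3 to 1: 5 | 26 |

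1 March lies in Period 3 for all three starts, so March onsets are placed correctly. No onset moves to a later period.

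**Stop-date cap.** It acts only when the imputed start is after the stop date. In every misplaced case the imputed start is too early, so a stop date in the true period leaves 7, 27, 26 and 48 unchanged.

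**Period-aware rule.** Take the latest period with a day that fits the known date parts and is not later than the report or stop date.

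- Report or stop date within the true period: 0 of 69 wrong for all three starts, with the day or the month missing.
- Visit of first report only, later period taken: Visit 7 spans Days 20–25 and Visit 12 spans Days 41–46, each across a dose. Onset Days 17–21 and 38–42 come after the preceding outpatient visit, so their next visit is one of these. Month missing: 5 + 5 = 10 wrong. Day missing: the 5 from Days 38–42 plus the 0, 1 or 2 February days that fall in Period 1, so 5, 6 or 7.
- Report date one period late and no stop date: day missing, the 21 Period 2 days plus 0, 1 or 2 February days of Period 1, so 21, 22 or 23; month missing, 21 + 21 = 42. These errors run to a later period.
- Neither date known: the latest compatible period also gives 21, 22, 23 and 42, against 7, 27, 26 and 48 now. That is no clear gain.

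**The case against.** The strongest reply is that the effect is conditional. SAP 8.3.2.2 does not say that imputed dates assign treatment, whereas SAP 8.3.3 and 8.3.4 do say how their imputed values are used. The SAP Introduction notes that "Related documents are the study protocol and electronic case report forms", and those forms, which are not available here, may record period or treatment. If they do, only the unstated attribution rule remains, and that alone is missing detail rather than a wrong rule. This stands.

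It is also fair that the first-dose rules serve to set TEAE status, and the status of true Period 2 and 3 events is not disturbed. Incomplete dates should be rare: Protocol 12.4 requires onset date and time, 12.5.1 has subjects questioned at each visit, and 14.2.1 asks for missing data to be explained. A missing month is particularly unlikely with scheduled contacts at most 7 days apart. All of this limits the size.

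A period-aware rule has its own error. The present rule never moves an event to a later period; the replacement can when a report is late. For an 11 January start with the day missing, the worst case is 21 days against 7 now. That stands as a cost and is why imputed onsets should be flagged.

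SAP 8.1 states that missing data are not imputed, which on its face conflicts with SAP 8.3.2. The specific date rules presumably govern, but the sentence should be reconciled with them.

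**Conclusion.** The point holds as a minor one. If AEs are assigned to treatment by onset date, the stated imputation rules put some Period 2 and 3 events under an earlier treatment: always Period 1 when the month is missing (onset year the same as the first-dose year) or the start is wholly missing with a stop date after first dose, and 7, 27 or 26 of 69 onset days when only the day is missing. The day-missing figures rest on planned dates and on treating 11 to 13 January 2021 as Day 1.

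Three stronger readings are not supported:

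- A reader might take 48 of 69 as an error rate. It counts calendar days under one pattern of missingness; the documents give no number of incomplete onsets.
- A reader might infer that one treatment gains. In the six sequences each treatment stands twice in each period, so with 4 subjects per sequence each is given to 2 × 4 = 8 subjects per period. Errors run to earlier periods but not systematically to any one treatment.
- A reader might take the by-treatment table to be wrong as planned. That needs assignment by onset date, which is the natural reading but is not stated.

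The overall column, the listing of all AEs and the PK analyses are unaffected.

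**What to change.** 1. **SAP 6.1.** Attribute each TEAE to the most recent dose taken at or before its onset or, for a TEAE that qualifies by worsening, at or before the worsening. State that an onset imputed to a dose date counts as after that dose.
2. **SAP 8.3.2.2.** Keep the present rules for onsets before the first dose. For other incomplete onsets with a known date of first report (with time on dosing days) or a complete stop date, take the latest period in which the subject was dosed that fits the known date parts and is not later than that report or stop. Impute that period's dose date or, if it is not in the known month, the first day of the known month within the period. Do not use visit number alone, because Visits 7 and 12 each straddle a dose.
3. Keep the stop-date cap, keep the present rule where neither date is known, and flag imputed onsets in the AE listing. The TEAE definition does not change.

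The cost is wording in two SAP sections and one listing flag, with no new assessment. The report date may have to come from source records for a few events. The new rule is a convention: a late report, or an AE that runs past the next dose without a known report date, can move an event to a later period, at worst over 21, 22 or 23 onset days with the day missing and 42 with the month missing.

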8.3.2.3 Missing Date Information for Prior or Concomitant Medications

For prior or concomitant medications, including rescue medications, incomplete (i.e., partly missing) start dates and/or stop dates will be imputed. When the start date and the stop date are both incomplete for a subject, the start date will be imputed first.

Incomplete Start Date

The following rules will be applied to impute the missing numeric fields for an incomplete prior or concomitant medication start date. If the stop date is complete (or imputed) and the imputed start date is after the stop date, the start date will be imputed using the stop date. Detail rules regarding the missing date information will refer to section 8.3.2.2 Missing Date Information for Adverse Events.

Incomplete Stop Date

The following rules will be applied to impute the missing numeric fields for an incomplete prior or concomitant medication stop date. If the date of the last dose of study treatment is missing, impute it as described in Section 8.3.2.1 Missing Date of the Last Dose of Study Treatment. If the imputed stop date is before the start date (imputed or non-imputed start date), the imputed stop date will be equal to the start date. Detailed rules regarding the missing date information are outlined in section 8.3.2.2 Missing Date Information for Adverse Events.

8.3.3 Missing Severity Assessment for Adverse Events

If severity is missing for an AE that started before the date of the first dose of study treatment, an intensity of mild will be assigned. If severity is missing for an AE that started on or after the date of the first dose of study treatment, an intensity of severe will be assigned. The imputed values for severity assessment will be used for the incidence summary; the values will be shown as missing in the data listings.

8.3.4 Missing Causal Relationship to study drug for Adverse Events

If the causal relationship to the study treatment is missing for an AE that started on or after the date of the first dose of study treatment, a causality of yes will be assigned. The imputed values for causal relationship to study treatment will be used for the incidence summary; the values will be shown as missing in the data listings.

8.3.5 Character Values of Clinical Laboratory Parameters

If the reported value of a clinical laboratory parameter cannot be used in a statistical summary table because, for example, a character string is reported for a parameter of the numeric type, a coded value must be appropriately determined for use in the statistical analyses. The actual values, however, as reported in the database will be presented in the data listings. Table 6 shows examples of how some possible laboratory results should be coded for the analysis.

Laboratory Test, SI Unit	Possible Laboratory Results	Coded Value for Analysis	
1 CHEMISTRY	•		
ALT, U/L	< 5	5	
AST, U/L	< 5	5	
Bilirubin, total, μmol/L	< 2	2	
URINALYSIS			
Glucose, mmol/L	$= OR > 55, \ge 55, > 0$	Positive	
	≤ 0 , negative	Negative	
рН	$> 8.0, \ge 8.0$	8.0	
	≥ 8.5	8.5	
Protein	$= OR > 3.0, \ge 3.0, > 0$	Positive	
	≤ 0	Negative	

Table 6. Examples of Coding Special Character Values for Clinical Laboratory Parameters

ALT = alanine aminotransferase; AST = aspartate aminotransferase; SI = *Le Système International d'Unités* (International System of Units).

